5. Non-invasive biomarkers of response or relapse during therapy with the aromatase inhibitor letrozole in combination with the CDK4/6 inhibitor ribociclib a. Serum cytokine levels

To seek for non-invasive biomarkers of response to therapy in relation to systemic and tumor-related immune reaction, we will measure cytokines serum levels at different time points. Cytokines are small proteins that are important in cell signaling. They are highly inducible peptides and mediate intercellular communication in the immune system ⁶². Alterations in specific cytokine expression patters have been detected in patients with breast cancer, and systemic inflammation has been associated with aggressive tumor growth, invasion and metastasis ⁶³. Therefore, serum cytokines levels represent promising non-invasive biomarkers to monitor patient's response to therapy and will be measured in this study. Measurement of cytokines will be performed at Akershus University Hospital using the Luminex platform as we previously described ⁶⁴.

b. Serum metabolite levels

Metabolites are small chemical compounds that are intermediates or products of metabolism. It is well known that cancer cells have a reprogrammed metabolism to convert nutrients to biomass while maintaining energy production. This phenomenon is increasingly recognized as a potential target for treatment, but also as a source for biomarkers that can be used for risk stratification, prognostication and therapy monitoring. In breast cancer, significant changes in the metabolism have been described, both in tumor tissue 65 and in biofluids 66. Our assessment of metabolites in the serum of the patients will therefore allow for the discovery of biomarkers as well as finding a connection between the microbiota and the host / systemic host metabolism. Indeed, the gut microbiota is involved in the regulation of numerous physiological pathways, among others

the energy metabolism is of particular interest. Metabolites will be measured using mass spectrometry as previously by collaborator in Trondheim (NTNU) as previously described 65 .

c. Circulating free tumor DNA (cftDNA)

Detection of circulating free tumor DNA (cftDNA) during follow-up after initial treatment for early breast cancer was associated with a high risk of relapse ⁶⁷. This gives the rationale to collect blood samples after surgery and end of treatment as it has strong potential to early detect the patients relapsing and or at risk of relapsing. Circulating free DNA will be extracted and sequenced at Akershus University Hospital.

RECRUITMENT TIME

Starting on December 1st. 2020 (or when the protocol is approved by local authorities and at the hospital level) until all patients are recruited (estimated recruitment period: 2 years).

SUBSEQUENT THERAPY

All patients treated following this protocol will be evaluated by an experienced breast surgeon for the best local surgical treatment option (breast conserving surgery or mastectomy including necessary procedures including the ipsilateral axilla).

After surgery, all patients will be considered for adjuvant treatment (both endocrine options and chemotherapy but also zoledronic acid etc.) according to

the national recommendations (Norwegian Breast Cancer Group; www.nbcg.net).

Patients with progressive diseases (at any time point) during neoadjuvant therapy or stable diseases following 3 months of therapy according to this protocol, will be able to obtain additional therapies (chemotherapy etc.) without any restrictions to allow down-staging prior to surgery by other means.

PROTOCOL AMENDMENTS AND SAE REPORTING

If necessary, protocol amendments will be done in collaboration with all involved parties and the regional ethical committee will be informed about all changes prior to implementation.

ADVERSE EVENT (AE) REPORTING

AE definition

An adverse event (AE) is defined as the appearance (or worsening in the case of pre-existing conditions) of any undesirable sign, symptom or disease that arises after having obtained the patient's informed consent, regardless of if it is considered to be related to the study drug. Any abnormal analytical values or test results occurring after obtaining informed consent shall only be reported in the eCRF under adverse events when there are clinical signs or symptoms, they are considered clinically relevant, they require treatment (for example, a hematological abnormality that requires transfusions or supportive therapy with hematopoietic stem cells) or require the study medication to be modified.

AEs that appear or worsen after obtaining the informed consent should be recorded in the eCRF under adverse events. Diseases that were already present at the time of granting informed consent must be recorded in the eCRF under medical history. Continuous monitoring for AEs will be carried out for at least 30 days after the last dose of the study treatment. The AEs (including the abnormal

analytical values constituting AEs) must be described by mentioning a diagnosis to the extent possible, instead of the underlying signs and symptoms. When no clear diagnosis can be identified, every sign or symptom must be reported as an independent AE.

The AEs shall be assessed in accordance with the Common Terminology Criteria for Adverse Events (CTCAE), version 4.03, whenever possible. In the event that a grade for an AE is not included in the CTCAE, the severity of mild, moderate, severe, potentially fatal and death shall be used, corresponding to grades 1 to 5. The onset of AEs should be investigated by asking the patient open-ended questions during the screening process after the signing of the informed consent and at each study visit. AEs can also be detected by spontaneous reporting by the patient during the screening process or between visits, as well as through the physical examination, analyses or other assessments. To the extent possible, all AEs must be assessed to determine:

- 1. Grade of severity (CTCAE grades 1 to 5).
- 2. Duration (dates of onset and finalization).
- 3. Relationship with the study treatment (reasonable likelihood that the AE is related: No/Yes; causality will be assessed individually for each study treatment).
- 4. Measure adopted with regard to the study treatment (none, dose adjustment, temporary discontinuation, permanent discontinuation, unknown, not applicable).
- 5. Administration of medication or treatment (absence of concomitant medication or nonpharmacological treatment, concomitant medication or non-pharmacological treatment).
- 6. Outcome (no recovery/no resolution, recovery/resolution, in recovery/being resolved, recovery/resolution with sequelae, fatal, unknown).
- 7. Seriousness, in accordance with the definition of serious adverse event (SAE) indicated in the section under.

All AEs must be treated appropriately. When a concomitant medication or non-pharmacological treatment is administered, this circumstance must be recorded in the eCRF under AE.

Once an AE is detected, it must be monitored until its resolution or until it is considered permanent; at each of the visits (or more frequently if necessary) the variation in the severity, the supposed relationship with the study treatment, the interventions needed to treat it and the outcome will be assessed.

With regard to determination of causality mentioned in point 3, the sponsor will subsequently classify the adverse event, on the basis of causality with the drug, according to the algorithm of Karch and Lasagna (1977), as:

- Definitive: there is a reasonable temporal sequence between administration of the drug and the appearance of the adverse event. This event coincides with the adverse event described for the drug, improves when it is interrupted and reappears after readministration and cannot be explained by alternative causes.
- Probable: there is a reasonable temporal sequence between
 administration of the drug and the appearance of the adverse event. This
 event coincides with the adverse event described for the drug, improves
 when it is interrupted and cannot be explained by alternative causes.
- Possible: there is a reasonable temporal sequence between administration of the drug and the appearance of the adverse event. This event coincides with the adverse reaction described for the drug, but may be explained by alternative causes.
- Conditional or unlikely: there is a reasonable temporal sequence between
 administration of the drug and the appearance of the adverse event. This
 event does not coincide with the adverse reaction described for the drug,
 and may be explained by alternative causes.
- Unrelated: there is no reasonable temporal sequence between administration of the drug and the appearance of the adverse event. This event does not coincide with the adverse reaction described for the drug, and may be explained by alternative causes.

Serious adverse events

Definitions

Serious adverse event (SAE) is defined as one of the following:

Is fatal or life-threatening

- Results in persistent or significant disability/incapacity
- Constitutes a congenital anomaly/birth defect
- Is medically significant, i.e., defined as an event that jeopardizes the
 patient or may require medical or surgical intervention to prevent one of
 the outcomes listed above
- Requires inpatient hospitalization or prolongation of existing hospitalization,

Note that hospitalizations for the following reasons should not be reported as serious adverse events:

- Routine treatment or monitoring of the studied indication, not associated with any deterioration in condition (i.e. to perform study related assessments)
- Elective or pre-planned treatment for a pre-existing condition that is unrelated to the indication under study and has not worsened since signing the informed consent
- Social reasons and respite care in the absence of any deterioration in the patient's general condition

Note that treatment on an emergency outpatient basis that does not result in hospital admission and involves an event not fulfilling any of the definitions of a SAE given above is not a serious adverse event

Reporting

AEs and SAEs

All reported adverse events and serious adverse events will be reported as defined in the previous section and recorded in the patient's eCRF.

SAEs must be reported by the investigator to national coordinating investigator as outlined in the ISF within 24 hours after the site has gained knowledge of the SAE. Every SAE must be documented by the investigator on the SAE pages in the eCRF, generating an automatic message to the national coordinating investigator and sponsor. The initial report shall promptly be followed by detailed, written reports if necessary. The initial and follow-up reports shall identify the trial subjects by unique code numbers assigned to the latter.

The sponsor keeps detailed records of all AEs and SAEs reported by the investigators and performs an evaluation with respect to seriousness, causality and expectedness.

Suspected Unexpected Serious Adverse Reaction (SUSARs)

SUSARs will be reported to the Competent Authority according to national regulation. The following timelines should be followed:

The sponsor will ensure that all relevant information about suspected serious unexpected adverse reactions that are fatal or life-threatening is recorded and reported as soon as possible to the Competent Authority and Ethics Committee, and in any case no later than seven (7) days after knowledge by the sponsor of such a case, and that relevant follow-up information is subsequently communicated within an additional eight (8) days.

All other suspected serious unexpected adverse reactions will be reported to the Competent Authority concerned and to the Ethics Committee concerned as soon as possible but within a maximum of fifteen (15) days of first knowledge by the sponsor.

SUSARs will be reported using the Council for International Organizations of Medical Sciences (CIOMS) form

The Sponsor is responsible for informing all investigators about SUSARSs occurring in the study on a regular basis.

Pregnancies

To ensure patient safety, each pregnancy in a patient on study treatment must be reported to the Sponsor within 24 hours of learning of its occurrence. The pregnancy should be followed up to determine outcome, including spontaneous or voluntary termination, details of the birth, and the presence or absence of any birth defects, congenital abnormalities, or maternal and/or newborn complications.

Pregnancy should be recorded on a Clinical Trial Pregnancy Form and send to the Sponsor.

Pregnancy follow-up should be recorded on the same form and should include an assessment of the possible relationship to the study treatment of any pregnancy outcome. Any SAE experienced during pregnancy must be reported on the SAE Report Form.

Pregnancy outcomes must be collected for the female partners of any males who took study treatment in this study. Consent to report information regarding these pregnancy outcomes should be obtained from the mother.

Study drug misuse or abuse

Any misuse or abuse of the Study drug must be reported to the Sponsor within 24 hours of learning of its occurrence.

Annual Safety Report

Once a year throughout the clinical trial, the sponsor will provide the Competent Authority with an annual safety report. The format will comply with national requirements.

ETHICAL CONSIDERATIONS AND APPROVALS

The protocol will be submitted to the regional ethical committee for approval prior to initiation of the study. There are no ethical conflicts connected to this protocol. The treatment provided has been tested in previous protocols and is known to be very effective in selected patients (as described in this protocol). The intention of the present protocol is solely to study the unknown mechanisms of tumor cell adaption during therapy in relation to the two drugs involved. As mentioned before, both drugs have been evaluated as highly potent and effective given in combination to breast cancer patients.

The design of the NEOLETRIB-trial has already been discussed with the Norwegian drug approval authority (Statens legemiddelverk – SLV) and we have

received the final evaluation from the responsible committee, confirming that NEOLETRIB may be initiated without further discussions with the SLV (due to the fact that all used drugs are approved in Norway for the treatment of breast cancer and no randomization is planned in NEOLETRIB).

DATA FLOW AND HANDLING

For all analyses to be conducted, patients will be recognized by a code number not allowing personal identification. The manual identifying each patient number by name will be kept locked in the Department of Oncology and is the responsibility of the principal corresponding investigator.

PUBLICATION OF DATA

All results will be published in relevant medical journals. Qualification for coauthorship will be decided by the principal investigator in collaboration with all involved partners in accordance with general practice (Vancouver-guidelines etc.).

FUNDING AND INVOLVED PARTIES

This trial is a research collaboration between the involved parties (UiO, AHUS and Novartis Norway AS), which involves study design, steering group participation and sharing of cost as regulated by the contracted agreement between the parties.

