Primary objective:

- 1. To evaluate the intra-tumor immunological effects of individual patients treated with letrozole and ribociclib in the neoadjuvant setting
 - a. Endpoints
 - i. Evolution of the intra-tumor immune profile during neoadjuvant therapy of breast cancer [*Time Frame: D1, D21, and at surgery*] determined through IHC or immunoblotting, scRNAseq, and other relevant methods described in the following chapters.

Secondary objectives:

- 1. To study early and late mechanisms of adaptation and resistance to aromatase inhibitor (letrozole) in combination with ribociclib;
 - b. Endpoints
 - i. Evolution of the tumor cell profile during neoadjuvant therapy of breast cancer [*Time Frame: D1, D21, and at surgery*] determined through whole tumor sequencing, scRNAseq etc.
- 2. To evaluate clinical and pathological response of targeted neoadjuvant therapy with letrozole and ribociclib
 - a. Endpoints
 - i. Determine the on treatment effects assessed by PEPI-0 and CCCA (Ki67<2,7%) at D 21 & at surgery. Change in Ki67 BL-

- D 21 to surgery, as well as ROR-score, based on genomic analysis. [Time Frame: D1, D21, and at surgery]
- ii. Long term effects and outcome will be assessed at yearly intervals in line with clinical routine.
- 3. To study the effect of ribociclib and letrozole treatment on the gut microbiome.
 - a. Endpoints
 - i. The longitudinal effect of neoadjuvant treatment will be determined through next generation amplicon sequencing on the V4 region of the fecal bacterial 16S rRNA gene by comparing baseline and follow up samples [Time Frame: D1, D21, D90 and at surgery (D180)]

- 4. To search for surrogate parameters (tumor- or immune related markers etc.) allowing to estimate the anti-tumor effects in liquid biopsies before and during therapy;
 - a. Endpoint:
 - i. Assess serum cytokine levels, serum metabolite levels and circulating free tumor DNA (cftDNA) [Time Frame: D1, D21, *D90* and at surgery (*D180*)]

Exploratory objectives:

- 1. To study the relationship between cancer treatment effect, the immune system and gut microbiota;
- 2. To develop optimal methods to evaluate the tumor response by novel CT / MRI techniques (tumor measurements);

Study Design: Multicentre, single-arm, open-label, neoadjuvant study;

Clinical Setting: Collaboration of two Norwegian Cancer Centers:

- Department of Oncology, Akershus University Hospital, Norway);
- 2. Department of Oncology, Drammen Hospital (Vestre Viken Health region, Norway);

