(additional breast cancer centers in Norway may be involved if patient recruitment is not reaching the expected pace);

Patients:

Patients diagnosed with (biopsy-confirmed) locally advanced (defined as either large T2, or T3/T4, or N2-3), ER-positive (≥50% pos. cancer cells), HER-2 negative, luminal-A/B breast cancer suitable for neoadjuvant antihormone therapy will be considered for this protocol; At least 100 patients should complete all study procedures. Thereafter, the protocol will be closed for further inclusion, but each patient included up to that time will be completed according to the protocol. The patients will be followed by the involved medical oncologists for up to 10 years after surgery or until relapse (whatever comes first).

Statistical considerations:

Based on the results of the CORALLEEN trial ¹ investigating neoadjuvant ribociclib treatment of luminal B patients, the spread between level of treatment response (24 weeks of treatment) based on MRI was 14% Complete Response (CR), 43% Partial Response (PR), 33% Stable Disease (SD) and 10% N/A. We propose a minimum sample size in either group to be at least >30 patients, thus an inclusion goal of 100 patients in total would be sufficient for hypothesis generating results. However, it is important to mention that the purpose of this trial is to deliver basic research results and not primarily to evaluate the efficacy or comparisons of treatments. Based on the major endpoints and their anticipated data variation, the data will be sufficient to come to reliable results. Finally, statistical power is added as all patients will serve as their own controls based on sequential intra-patient data obtained over time (in general 180 days all in all).

This is aligned with advice given by gastroenterologists and on par with earlier studies that allowed for characterization of the tumor immune microenvironment and the gut microbiota ^{2,3} and gives sufficient statistical power to prioritize biomarkers for larger companion diagnostic studies in the future.

Treatment:

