All cancer drugs used in this trial (letrozole, ribociclib, goserelin) are well-established in MBC and have also proven high efficacy in previous neoadjuvant trials in locally advanced breast cancer, both as monotherapy and in combination ^{4,49-58}. Thus, it is known that most of the patients will have clinical benefit from these medications and many will be able to avoid neoadjuvant/adjuvant chemotherapy that is associated with considerable more serious side-effects compared to study medication. However, if patients do not profit sufficiently from the medication given in this trial, they will be taken off study medication and be treated with all available types of standard chemotherapy established for these patients (no restrictions caused by the present protocol). In addition, all patients will be considered for adjuvant therapy according to the final pathological report following surgery (yTNM-status) and according to the Norwegian breast cancer guidelines published by the Norwegian Breast Cancer Group (www.nbcg.net).

MEDICAL EVALUATIONS and SAMPLING

Clinical evaluations

In general, patients will be followed at the outpatient clinics (Akershus University Hospital, Department of Oncology & Drammen Hospital, Department of Oncology) by experienced medical breast cancer oncologists at least every 4 weeks during the entire study (including caliper measurements of maximum tumor diameters). In addition, measurement of maximum tumor diameters will be performed at study entry and during therapy every 3 months by advanced MRI (ax T1, T2, DWI, dynamic study and spectroscopy) and Spectral-CT scans at

the Departments of Radiology, Akershus University Hospital and Drammen Hospital. All measurements (MRI, spectral-CT etc.) will be performed always prior to biopsies at baseline and before final surgery as usual to avoid that bleeding etc. may interfere with the diagnostic procedures. Patients will be informed about the opportunity to perform PET-scanning prior to treatment after protocol as a general screening procedure for distant metastasis (not mandatory). All patients will be screened for distant metastasis by CT-scanning (thoracic, abdominal and pelvic CT-scanning as well as a bone-scintigraphy) at study entry. All available additional diagnostic procedures may be used at the discretion of the responsible oncologists / breast cancer surgeons (not mandatory).

Blood samples (scientific samples)

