Blood samples will be drawn preferably in the morning following an overnight fast (not mandatory but recommended) at the following time points:

- 1st.. blood sample: on days 7 to 1 (but before the first treatment after protocol; day 1 = day of the first tablets)
- 2nd. blood samples: day 21;
- 3rd. blood sample: following 3 months on therapy (+/- 7 days);
- 4th. blood sample: following 6 months on therapy (+/- 7 days);
 (whenever possible during on of the last days of the ongoing ribociclib cycle);
- Additional blood samples: every 3 months (if treatment > 6 months);
- After surgery: once every year for 5 years;
- At relapse/metastasis;

Blood samples per timepoint include: 2 x 10 ml of heparin-plasma; 2 x 10 ml EDTA-plasma (cells will be kept in separate vials); 2 x 10 ml serum; 2 x 10 ml of citrate-plasma; 2 CPT vials and 4 x 10 ml of full-blood (EDTA). These scientific blood samples will be spinned as usual and stored at -80°C at the individual research departments (EPIGEN-center, Akershus University Hospital; Research unit at Drammen Hospital) until processing.

In addition, all standard established blood samples (liver samples, kidneyfunction, bone-marrow function etc.) will be taken as usual and recommended for the treatment with aromatase inhibitors in combination with ribociclib. Detailed instructions for the handling of scientific blood samples are summarized in the appendix of this protocol.

Tissue samples

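### Long-term follow-up runs from surgery to first relapse, leaving treated patients who are never operated, and events after relapse, without a follow-up plan

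*Combined protocol and SAP*

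**What the plan says.** - **Follow-up period** (Short Summary, Patients): "The patients will be followed by the involved medical oncologists for up to 10 years after surgery or until relapse (whatever comes first". Surgery is the only stated start. Relapse or ten years is the end.
- **Long-term endpoint** (secondary objective 2, endpoint ii): "Long term effects and outcome will be assessed at yearly intervals in line with clinical routine". It names no event, time origin, population or censoring rule.
- **Research blood samples** (Blood samples): the long-term series is "After surgery: once every year for 5 years". A separate item reads "At relapse/metastasis", and nothing is scheduled after it.
- **Insufficient benefit** (Patients and Treatment, Treatment): "they will be taken off study medication and be treated with all available types of standard chemotherapy established for these patients".
- **Progression, or stable disease at three months** (Subsequent Therapy): "Patients with progressive diseases (at any time point) during neoadjuvant therapy" are mentioned together with stable disease. Both groups may receive other therapy "without any restrictions to allow down-staging prior to surgery by other means".
- **Surgical assessment** (Subsequent Therapy): "All patients treated following this protocol will be evaluated by an experienced breast surgeon for the best local surgical treatment option".
- **Safety follow-up** (Adverse Event Reporting): at least 30 days after the last dose.

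**The concern.** Treatment lasts at least six months before surgery, and the protocol itself foresees patients who progress or leave study drug in that time. Some of them may develop metastases, remain inoperable, decline surgery or die first. For these patients the follow-up clock never starts. Patients who switch therapy and are operated later do enter follow-up, but at unequal times from first dose.

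At the other end, stopping at relapse means that distant spread after a local relapse, and death after any relapse, are not planned data.

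The outcome is therefore conditioned on reaching surgery. This also matters if day 1 or day 21 markers are related to long-term outcome. A clock that starts at surgery compares only patients who got through the following months and were operated, so the early failures have samples but no linked long-term result.

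**Working it through.** **The plan's own figure.** The protocol gives no event rate, event count or precision for the long-term outcome, so there is nothing to reproduce. Its target of 100 patients rests on response groups of more than 30 and has no bearing on this point. Every input below is an assumption, shown as a range.

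**1. Starting at surgery.** Let f be the share of treated patients never operated, S the 5-year event-free survival of operated patients, and S0 that of unoperated patients. For simplicity both are put on one clock.

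- Whole cohort: (1 − f) × S + f × S0
- Overstatement if only operated patients are reported: S − [(1 − f) × S + f × S0] = f × (S − S0)

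Example: f = 0.10, S = 0.90, S0 = 0 gives a whole-cohort value of 0.90 × 0.90 = 0.81, so the overstatement is 9.0 points.

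| S | f | S0 = S | S0 = 40% | S0 = 0 |
|---|---|---|---|---|
| 80% | 2% | 0 | 0.8 | 1.6 |
| 80% | 5% | 0 | 2.0 | 4.0 |
| 80% | 10% | 0 | 4.0 | 8.0 |
| 90% | 2% | 0 | 1.0 | 1.8 |
| 90% | 5% | 0 | 2.5 | 4.5 |
| 90% | 10% | 0 | 5.0 | 9.0 |

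Entries are percentage points. With f = 0 the overstatement is zero throughout.

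**2. Stopping at relapse.** The effect depends on the endpoint.

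- *Relapse-free survival among operated patients:* relapse is the event, so nothing after it is needed and there is no bias.
- *Overall survival:* deaths after relapse are missing. Suppose it were estimated by censoring at relapse. With constant yearly hazards r (relapse), d = 0.01 (death without relapse) and p (death after relapse), and a = r + d:
  - True survival at t: exp(−a t) + [r / (a − p)] × [exp(−p t) − exp(−a t)]
  - Estimate with censoring at relapse: exp(−d t)

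Example: r = 0.02, p = 0.20, t = 5 gives exp(−0.15) = 0.861, plus (0.02 / −0.17) × (0.368 − 0.861) = 0.058, so true survival is 0.919. The censored estimate is exp(−0.05) = 0.951.

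| r | p | Year | True | Censored at relapse | Overstated (points) |
|---|---|---|---|---|---|
| 0.02 | 0.20 | 5 | 91.9% | 95.1% | 3.3 |
| 0.02 | 0.20 | 10 | 81.2% | 90.5% | 9.3 |
| 0.03 | 0.25 | 5 | 89.5% | 95.1% | 5.6 |
| 0.03 | 0.25 | 10 | 75.4% | 90.5% | 15.0 |
| 0.05 | 0.35 | 5 | 83.9% | 95.1% | 11.3 |
| 0.05 | 0.35 | 10 | 63.8% | 90.5% | 26.7 |

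Differences were taken before rounding. The table shows why such an estimate would be invalid. The protocol does not propose it.

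**The case against.** The protocol nowhere says that unoperated patients are excluded. It is silent on them, and endpoint ii itself names neither surgery as origin nor an operated-only population. Several stronger readings are tempting and do not hold.

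- *Stopping study drug removes a patient.* It does not. Subsequent Therapy still aims such patients at surgery and has every treated patient seen by a surgeon. The gap concerns only those never operated, whose number is not given.
- *Deaths and metastases outside the window go unrecorded altogether.* Too broad. Sampling at relapse or metastasis is listed separately from the post-surgery series. Fatal events are reported as serious adverse events until at least 30 days after the last dose. Death without relapse after surgery falls within follow-up.
- *The biomarker objectives lose their early failures.* Secondary objectives 1 and 4 have time frames that end at surgery. Response is assessed clinically every 4 weeks and by MRI every 3 months, and the Tissue samples section wants the six-month biopsy from all patients. The loss concerns only links from those markers to long-term outcome.
- *No survival result by marker can be reported.* Relapse-free survival from surgery can be, and it is a legitimate quantity for operated patients.

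It is also fair to say that overall survival is not a named endpoint, and that the trial describes itself as basic research and hypothesis-generating rather than primarily a test of efficacy.

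These points narrow the concern but do not remove it. Aiming at surgery is not the same as reaching it. The sentence in the Short Summary is also the only working rule for a secondary endpoint that is otherwise undefined.

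**Conclusion.** The point holds in limited form. Followed exactly, the protocol yields a long-term outcome for operated patients up to first relapse. It cannot give a valid event-free result for all treated patients, overall survival, or distant-metastasis-free survival beyond a first local relapse.

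A reader might infer that long-term results will certainly look too good. The documents do not support that. Upward bias is the likely direction if unoperated patients do worse, and its size depends on a share that the protocol does not state. On the assumed inputs it is 0 to 9 points in 5-year event-free survival, and zero is a possible value. The overall survival figures (about 3 to 11 points at 5 years, 9 to 27 at 10 years) apply only if someone later estimated it by censoring at relapse.

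Because this is one secondary endpoint in a single-arm, exploratory trial, the change is a cheap improvement and not a condition for the trial's validity.

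**What to change.** 1. **Short Summary, Patients:** follow every treated patient from day 1 for the planned period, regardless of early stopping, switch of therapy or absence of surgery.
2. **Secondary objective 2, endpoint ii:** define the long-term endpoint as event-free survival from day 1 in all treated patients. Events are progression precluding surgery, relapse, distant metastasis and death. State the censoring rule. Keep relapse-free survival from surgery, in operated patients, as a supplementary result.
3. **After relapse:** record vital status and distant metastasis once a year from routine records, to the end of the planned period.
4. **Day 21 markers:** if they are related to long-term outcome, count time from day 21 (a landmark analysis).

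No treatment rule changes, and no extra visits or procedures are needed. The cost is a light yearly record check for unoperated and relapsed patients and a protocol amendment, of which the ethics committee must be informed before implementation. It should be confirmed that consent covers the added records. The reported event rate may be slightly less favourable.
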